5.2 Analysis of feasibility outcomes

Feasibility outcomes will be summarised using mean (SD) and median (IQR) for continuous variables and n (%) for categorical variables.

5.2.1 Analysis of study logistics parameters

Feasibility Outcomes	Analysis	
Recruitment	The average rate of eligible participants presenting to MSK hubs per month	No. of eligible participants presenting to MSK hubs during recruitment period/ length of recruitment period (in months)
	Proportion of eligible participants clinicians are willing to recruit	No. of eligible participants clinicians are willing to recruit/ no. of eligible participants presented to MSK hubs
	Proportion of eligible participants randomised	No. of eligible participants randomised/ no. of eligible participants presented to clinicians
Adherence	Participant adherence to study protocol	No. of participants receiving injections / no. of randomised participants
Retention	General retention	No. of participants who provided any follow-up data / no. of randomised participants for study visits listed in section 3.2, overall and by treatment groups
	OSS questionnaire retention	No. of participants who answered any OSS items / no. of randomised participants for study visits listed in section 3.2, overall and by treatment groups

Data completeness	Proportion of missingness in each outcome at each time point (as specified in section 3.2), overall and by reasons of missingness (where available):	No. of participants who provided complete outcome (usable in analysis without imputation)/ no. of randomised participants
	Proportion of randomised participants who returned resource use questionnaire, by study visits, overall and by reason of missingness (where available):	No. of randomised participants who returned resource use questionnaire/ no. of randomised participants for study visits listed in section 3.2 where such a questionnaire is due
	Proportion of randomised participants who were successfully linked to administrative primary care records	No. of randomised participants successfully linked to administrative primary care records/ no. of randomised participants
	Proportion of randomised participants who were successfully linked to administrative hospital care records	No. of randomised participants successfully linked to administrative hospital care records/ no. of randomised participants
Data concordance	Proportion of discrepancy in demographic variables (age, gender, ethnicity, smoking, and alcohol history)	No. of participants with inconsistent answers/ no. of randomised participants with available linked data, by demographic variables of interest
	Proportion with reported resource use	No. with reported resource use /no. of randomised participants with returned or linked data for resource use categories listed in section 3.2, by study visit
	Rate of reported resource use	No. of reported resource use items (consultations, medications)/ no. of randomised participants with returned or linked data for resource use categories listed in section 3.2, by study visit

5.2.2 Analysis of feasibility of self-measuring ROM

Agreement between self-measured and clinician-measured ROM at 6 weeks (flexion and external rotation respectively) will be assessed using the Bland and Altman's method.

Differences between the two methods of measurements will be plotted against their means. An overall mean difference (or bias) will be marked on the graph.⁸ Regression-based estimates of 95% limits of agreement will be plotted on the graph using STATA command blandaltman.

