4.2 Randomisation procedure

Randomisation will only occur when the research team confirms eligibility, and the participant has provided written, informed consent.

Participants will be randomised in a 1:1:1:1 ratio, stratified by recruiting centre, to one of the following:

- CSI&HD and patient to self-measure ROM self-measured before 6 week (+/- 3 days) visit
- CSI&HD and patient to self-measure ROM self-measured after 6 week (+/- 3 days) visit
- CSI alone and patient to self-measure ROM self-measured before 6 week (+/- 3 days) visit
- CSI alone and patient to self-measure ROM self-measured after 6 week (+/- 3 days) visit

The allocation will be determined just prior to the time of the injection, using a web-based, distant randomisation service administered by the Pragmatic Clinical Trials Unit, QMUL. Allocation lists using random permuted blocks of sizes 4 and 8 will be prepared by the trial statistician with the final lists being uploaded to the randomisation system by an independent statistician.

The clinician providing the injection will contact a member of the research team once the participant has arrived for their appointment. The research team member who is appropriately and sufficiently trained and delegated to complete randomisation will randomise the patient and communicate the allocation to the treating clinician.

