6.4 Graphs

We will create a plot tracking the changes in treatment effect (mean OSS difference) and its 95% CIs throughout study.

We will create a Bland-Altman, regression-based, difference-vs-mean plot assessing the agreement between self-measured and clinician-measured ROM.

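### The order of self-measured and clinician-measured ROM is randomised, but no planned analysis uses it, so the single pooled agreement result cannot show an order effect

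*SAP*

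**What the plan says.** Section 4.2 of the SAP states "Participants will be randomised in a 1:1:1:1 ratio, stratified by recruiting centre". The four cells are the two treatments crossed with the timing of self-measurement. One cell, for example, is "CSI&HD and patient to self-measure ROM self-measured before 6 week (+/- 3 days) visit" and another is "CSI alone and patient to self-measure ROM self-measured after 6 week (+/- 3 days) visit". The timing of self-measurement relative to the 6-week visit is therefore a randomised factor in its own right.

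The agreement analysis is in section 5.2.2: "Agreement between self-measured and clinician-measured ROM at 6 weeks (flexion and external rotation respectively) will be assessed" by the Bland-Altman method. Its outputs are a bias line ("An overall mean difference (or bias) will be marked on the graph") and limits ("Regression-based estimates of 95% limits of agreement will be plotted on the graph using STATA command blandaltman"). Section 6.4 plans a "regression-based, difference-vs-mean plot assessing the agreement between self-measured and clinician-measured ROM". Neither section mentions order. Table 8, the dummy table for ROM at the 6-week visit, has columns for treatment group only, and section 5.5 rules out subgroup analyses.

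**The concern.** A design that randomises the order of two measurements normally does so to examine, or at least display, whether order matters. Here the factor is created at randomisation and then not used. A participant who self-measures after the visit has recently been measured by a clinician; one who self-measures before it has not yet been measured at that visit. If the first measurement influences the second, the two halves have different biases, different spreads, or both. A single bias and a single set of limits then describe neither half, and nothing in the planned output would reveal it.

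Section 3.2 offers self-measurement as the way to collect ROM when follow-up is remote, and the 12- and 26-week visits are remote. Section 5.2.2 is the SAP's quantitative check of that method, so its result bears on whether self-measured ROM is carried into the full trial. The stakes are limited, because the proposed primary outcome for that trial is the Oxford Shoulder Score.

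**Working it through.** The SAP states no figure for agreement, so there is none to reproduce. The check has three parts.

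**1. Tracing the factor**

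| Place in SAP | Use of order |
|---|---|
| 4.2 Randomisation | Defines it, crossed with treatment |
| 5.2.2 Agreement analysis | None; one overall bias, one set of limits per movement |
| 5.5 Subgroups | None planned |
| 6.4 Graphs | None |
| Table 8 | Split by treatment only |

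The SAP does not use the word pooled. Pooling is inferred from the overall bias line and from the absence of any order term, stratum or table. Regressing the difference on the mean, as the regression-based limits do, does not separate the two orders.

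**2. What pooling could do (illustration; k, D and the SD are assumed)**

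Let s be the SD of the self-minus-clinician difference in the before-visit half, with equal numbers in each order. Constant-SD limits are used for simplicity.

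*Case A: differences shrink in the after-visit half by a fraction k.*
- Pooled SD / s = sqrt((1 + (1 − k)²) / 2), taking zero mean bias.
- Pooled bias / before-visit bias = 1 − k/2, if there is a bias.

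| k | Pooled SD / s | Pooled limits narrower by | Pooled bias as share of before-visit bias |
|---|---|---|---|
| 0.25 | 0.884 | 11.6% | 87.5% |
| 0.50 | 0.791 | 20.9% | 75% |
| 0.75 | 0.729 | 27.1% | 62.5% |
| 1.00 | 0.707 | 29.3% | 50% |

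With a nonzero before-visit bias b, the pooled variance gains (kb)²/4, which offsets some of the narrowing.

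*Case B: only the bias shifts, by D, with the same SD in both orders.*
- Pooled SD = sqrt(SD² + D²/4).
- SD 8 degrees, D 5 degrees: sqrt(64 + 6.25) = 8.38; limits ±1.96 × 8.38 = ±16.4.
- SD 8 degrees, D 10 degrees: sqrt(64 + 25) = 9.43; limits ±18.5.
- Within either order: ±1.96 × 8 = ±15.7.

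At D = 10 the pooled limits are 18.5/15.7 = 1.18 times the within-order limits, and the pooled bias is 5 degrees away from the bias in each order.

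The two cases move the limits in opposite directions, so the direction of any error cannot be stated in advance.

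**3. Precision if results are split by order**

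Inputs: 66 participants (section 4.1), hence 33 per order. Section 4.1 gives 15% attrition for the definitive trial. Applying it here is an assumption: 66 × 0.85 = 56, or 28 per order.

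95% CI half-widths, in units of the SD of the differences:
- Mean difference: t / sqrt(n).
- Each limit: t × sqrt(1/n + 1.96² / (2(n − 1))), the constant-SD approximation.
- Between-order difference in bias: t × sqrt(2/n), with n per order and 2n − 2 degrees of freedom.

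| Pairs | Mean difference | Each limit |
|---|---|---|
| 66 pooled | 0.25 | 0.42 |
| 56 pooled | 0.27 | 0.46 |
| 33 in one order | 0.35 | 0.61 |
| 28 in one order | 0.39 | 0.67 |

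The between-order difference has half-width 0.49 SD (33 per order) or 0.54 SD (28 per order). At the assumed SD of 8 degrees that is 3.9 or 4.3 degrees.

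**The case against.** The best defence of the plan is that equal allocation balances order. That holds for symmetric effects: if the shoulder truly changes between the two measurement dates, the shifts in the two halves cancel in the overall mean. It does not hold for carry-over, which acts only on those who self-measure second; balance averages that effect and does not remove it. Even a symmetric shift still widens the pooled limits, as in case B.

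A second defence is that carry-over is undocumented. The SAP does not say whether participants are told the clinician's reading, whether they are coached, or how long after the visit they self-measure. This stands: carry-over is a possibility, and its size is unknown.

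A third is that a small feasibility study is better served by one pooled estimate. This stands in part. It is a reason to keep the pooled result, but not a reason to omit a descriptive split.

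A reader might infer two stronger conclusions that the SAP does not support. The first is that pooling makes agreement look better than it is; the error can go either way. The second is that only the before-visit group reflects remote use, so the conclusion should rest on it. Table 6 provides for researcher and participant ROM readings at baseline, so that group is not naive to measurement. The remote visits also follow the 6-week clinician measurement in both orders. Neither order reproduces remote follow-up exactly.

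**Conclusion.** The SAP randomises the order of measurement and then plans no analysis, table or graph that uses it. That omission is clear from the text. As planned, the agreement result could average two different biases and attach limits that are too narrow or too wide, without any sign of it.

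The size cannot be derived from the SAP. The illustrations run from pooled limits 29% narrower than the before-visit limits (complete shrinkage, no mean bias) to 18% wider than the within-order limits (a 10-degree shift with SD 8). These rest on assumed values and on constant-SD limits, whereas the SAP specifies regression-based ones. The data could show a large order difference in bias, of about half an SD or more, but not a small one.

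**What to change.** Keep the pooled Bland-Altman analysis and add the following to sections 5.2.2 and 6.4, for flexion and external rotation separately:

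- mean difference and 95% limits of agreement by randomised order;
- order marked on the plots, for example by different symbols;
- the between-order difference in bias with a 95% CI, reported descriptively and without a significance test, in keeping with section 5.3.

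Add a short dummy table for these results, and state in section 5.5 that this display of a randomised measurement factor is not a treatment subgroup analysis. Discuss any order difference when judging self-measured ROM for remote visits, without a rule that the conclusion rests on one order. The discussion should note that a between-order difference may combine carry-over, practice and true change between the two dates.

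The cost is a few lines of code and one table; no new data are needed. The drawback is precision: with about 28 to 33 pairs per order, each within-order limit has a 95% CI half-width of about 0.6 to 0.7 SD, against 0.42 to 0.46 SD pooled.

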5.3 Analysis of clinical and health economics outcomes

Descriptive statistics will be used to summarise all clinical and health economics outcome measures at each time point in each group.

As this is a feasibility study and the sample size is small, there will be no significance testing, except for circumstances described in 5.3.1, where the definitive trial is deemed infeasible.

Complete case analyses are assumed unless otherwise specified.

For Oxford Shoulder Score (OSS):

- Mean (SD) and median (IQR) will be presented for each group at each time point
- Sensitivity analyses will be conducted on mean (SD) and median (IQR) by presenting and comparing statistics derived using different methods of imputation on individual missing items (see 5.6 for more details)
- Percentage of missing will be presented for each group at each time point

For range of motion (ROM) – forward flexion:

- Mean (SD) and median (IQR) will be presented for each group at each time point
- Percentage of missing will be presented for each group at each time point

For range of motion (ROM) – external rotation:

- Mean (SD) and median (IQR) will be presented for each group at each time point
- Percentage of missing will be presented for each group at each time point

For each domain of health-related quality of life (EQ-5D-5L):

- Proportion of participants at each level
- Percentage of missing will be presented for each group at each time point

For health-related quality of life (EQ-5D-5L) summary index:

- Mean (SD) and median (IQR) will be presented for each group at each time point
- If the score for a domain is missing, then the overall index would be treated as missing
- Percentage of missing will be presented for each group at each time point

For health-related quality of life (EQ-5D-5L) VAS score:

- Mean (SD) and median (IQR) will be presented for each group at each time point
- Percentage of missing will be presented for each group at each time point

For cost of resources used (2023£): healthcare costs, personal care costs, time-off-work costs, out-of-pocket costs

- Mean (SD) and median (IQR) will be presented for each group at each time point

- Percentage of missing will be presented for each group at each time point

5.3.1 Analysis of OSS if full trial is not feasible

If a trial is not deemed feasible the primary analysis will investigate mean differences in OSS between the treatment arms at each follow-up time point on an intention to treat basis.

The analysis will use a mixed-effects repeated measures model with restricted maximum likelihood estimation. Patient level random effects will not be specified. Instead, an unstructured covariance matrix for the residual errors will be used to model correlation within repeated measures.⁹ Observations from different participants are assumed independent. Satterthwaite approximation for degrees of freedom will be used to avoid upward bias of type I error due to the relatively small sample size.¹⁰⁻¹¹ Gender, age, site and baseline OSS will be adjusted for in the model as fixed effects. An interaction effect between post-randomisation time point (as a categorical variable) and baseline OSS will be fitted. An interaction effect between the randomised treatment group and post-randomisation time point will also be fitted to allow for a saturated model for the mean at each time point for each treatment group.⁹ Missing baseline OSS scores will be imputed using mean imputation.

ROM and EQ-5D will be analysed using the same mixed-effects model as specified for OSS or an equivalent model appropriate for the outcome type.

Strategy for analysis of clinical outcomes if full trial is not feasible and if the above model fails to converge:

1. Remove interaction effects between visits and baseline OSS
2. Remove fixed effect gender
3. Remove fixed effect age
4. Remove fixed effect Site
5. Remove main fixed effect baseline OSS
6. Forgo mixed-effects repeated measures model and adopt simple between group t-tests at each time point

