5.6 Sensitivity analyses

Different approaches for individual item missingness in OSS will be compared. Single imputation where missing items for a participant's OSS are substituted by the mean of their provided OSS items will be conducted. Furthermore, multiple imputation will be applied to individual items missing in the 12-item OSS questionnaire, assuming missing at random.

This will be done at each time point respectively for sets of results where there are no more than 2 items missing², as well as sets of results where there is at least 1 item completed.

Summary statistics derived will be presented together with summary statistics derived under complete case analyses for comparison (see table 13).

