Appendix 1: Flow-diagram

Appendix 2: Derivation of all outcome measures

1. Feasibility outcome – recruitment

Proportion of eligible participants clinicians willing to recruit:

- No. of eligible participants clinicians willing to recruit/ no. of eligible participants presented to MSK hubs

Eligible participants clinicians are willing to recruit may refused to be recruited before randomisation. Therefore, to compute the no. of eligible participants clinicians are willing to recruit, we add the total number of participants clinicians recruited (total number of participants eventually randomised) and the total number of eligible participants who refused to be recruited.

2. Oxford Shoulder Score (OSS)

The OSS is a validated patient self-reported instrument developed with patients, including those with frozen shoulder¹; it has been used in randomised trials of patients with frozen shoulder and in long-term follow-up studies.²

The OSS is a 12-item measure. Each of the 12 items has 5 potential answers and is scored from 4 (best/fewest symptoms) to 0 (worst/most severe). The total score is the sum of the 12 individual items and therefore ranges from 0 to 48; lower score indicates greater degree of disability.^{1,3}

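### One blank OSS item makes the whole form missing in the 5.3.1 model and the 6.1 AUC, because the item-level methods in 5.6 reach only the descriptive Table 13

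*SAP*

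**What the plan says.** Section 5.3, which contains 5.3.1, sets the default: "Complete case analyses are assumed unless otherwise specified". Appendix 2 defines the score: "The total score is the sum of the 12 individual items and therefore ranges from 0 to 48". It gives no rule for a form with a blank item.

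Section 5.3.1 specifies a repeated measures model for OSS, with baseline OSS as a covariate and in an interaction with time point. Its one departure from complete case is: "Missing baseline OSS scores will be imputed using mean imputation". Nothing is said about follow-up forms with blank items.

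Section 5.6 describes two item-level methods. The first is: "Single imputation where missing items for a participant's OSS are substituted by the mean of their provided OSS items will be conducted". The second is: "multiple imputation will be applied to individual items missing in the 12-item OSS questionnaire, assuming missing at random". Each is applied to "sets of results where there are no more than 2 items missing", and separately to forms with at least one answer. The output is limited: "Summary statistics derived will be presented together with summary statistics derived under complete case analyses for comparison", with a pointer to Table 13. Table 14, which holds the model results, has a single OSS block and no imputed version. Section 6.1 builds its AUC statistics from the 5.3.1 parameter estimates.

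**The concern.** OSS is the proposed primary outcome of the definitive trial. Under these rules the model ignores answers that participants have given. A participant who answers 11 of 12 baseline items gets a mean of the scores in place of a total already known to within 4 points. A follow-up form with 11 answers contributes nothing at that visit.

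In a study of 66 people this costs precision in the only inferential analysis in the plan, and in the AUC estimates meant to inform the full-trial sample size if AUC becomes the primary outcome. If people with worse (or better) function skip items more often, dropping their follow-up forms could also bias the comparison. The SAP names no benefit from this, and the scoring code that would avoid it is already needed for Table 13.

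**Working it through.** **Does one blank item make the score missing in the model?** The SAP states no figure that depends on this rule, so the texts are set side by side.

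- The default in 5.3 is complete case, and 5.3.1 sits under it.
- The total in Appendix 2 needs all 12 items.
- Table 13 lists complete cases separately from forms with at most two blanks, so a form with one gap is not a complete case.
- 5.3 describes the OSS sensitivity analyses as analyses of means (SD) and medians (IQR), and 5.6 points to Table 13. Neither mentions the model.
- The exception in 5.3.1 concerns baseline scores, not items. The type of mean (overall, by arm, by site) is not given; a mean of the scores is the ordinary reading, since 5.6 words person-mean substitution differently.

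Together these give the rule described above.

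**Illustration.** Eleven baseline answers summing to 6: the true total lies between 6 and 10, and person-mean scoring gives 12 × 6/11 = 6.5. The plan would enter the mean of the scores instead, for example 20 if that were the sample average (assumed). A follow-up form with 11 answers summing to 40 has a true total between 40 and 44; person-mean scoring gives 12 × 40/11 = 43.6. The plan drops it.

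**How many forms?** Assume each item is blank independently with probability q.

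- P(at least one blank) = 1 − (1 − q)^12
- P(one or two blank) = 12q(1 − q)^11 + 66q²(1 − q)^10

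| q (assumed) | At least one blank | One or two blank | Forms affected if all 66 return one |
|---|---|---|---|
| 0.5% | 5.8% | 5.8% | 3.9 |
| 1% | 11.4% | 11.3% | 7.5 |
| 2% | 21.5% | 21.4% | 14.2 |

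Almost every affected form falls within the two-item threshold that 5.6 already uses.

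**Error in a baseline score.** Assume 12 exchangeable items with Cronbach alpha a from 0.80 to 0.95. The inter-item correlation is r = a/(12 − 11a), which gives 0.25 to 0.613. Relative to the SD of the total, the root mean squared error of person-mean scoring is:

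- one blank: √[(1 − r)/(11(1 + 11r))] = 0.135 at r = 0.25, and 0.067 at r = 0.613
- two blank: √[0.2(1 − r)/(1 + 11r)] = 0.20 and 0.10

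Replacing the score by the sample mean has an error of about 1 SD. For one blank item that is roughly 7 to 15 times larger (1/0.135 and 1/0.067).

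**Effect on the treatment comparison, baseline.** With 11.4% of baselines replaced at random and an assumed baseline/follow-up correlation ρ, the standard error ratio is √[(1 − 0.886ρ²)/(1 − ρ²)]. This is 1.006 at ρ = 0.3, 1.02 at ρ = 0.5 and 1.05 at ρ = 0.7.

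**Effect on the treatment comparison, follow-up.** If a share p of scores is dropped at one visit, the single-visit standard error rises by 1/√(1 − p):

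- p = 5.8%: 1.03
- p = 11.4%: 1.06
- p = 21.5%: 1.13

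These are upper bounds for the follow-up loss, because the model keeps the participant's other visits and recovers some information from them.

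**The case against.** The strongest objection is that the SAP never says outright that one blank OSS item voids the score. It does say so for a missing EQ-5D domain. That stands as a caveat: the rule is inferred from the default, the 12-item sum and the layout of Table 13. But if the inference were rejected, nothing would say which of the five OSS versions in Table 13 enters the model, and the choice would be left until data are seen. A sentence is needed either way.

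The setting is also limited. Inference from 5.3.1 takes place only if the full trial is judged infeasible, and the AUC in 6.1 is exploratory. This lowers the stakes but does not remove the point.

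The assumed independence of gaps matters too. If blanks cluster within people, fewer forms are affected at the same item rate, so the shares above lean high.

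Three stronger readings are tempting, and the document does not support them:

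- A reader might infer that 5.6 has already settled an item-level rule that 5.3.1 ignores. It has not: it compares two methods at two thresholds and chooses none. Comparing them is a legitimate feasibility aim.
- A reader might infer that the full-trial sample size in 6.6 will be inflated for item-level loss. The default in 5.3 does not govern 6.6, which does not say how the paired differences are scored and takes data availability from an estimand that 6.2 leaves to the report. Section 3.1 also defines OSS retention by any answered item.
- A reader might infer that mean imputation at baseline biases the treatment effect. In a randomised comparison it mainly costs precision, and modestly so on the figures above.

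**Conclusion.** The point holds for the 5.3.1 model and the 6.1 AUC. Read together, the stated rules discard a partly answered follow-up form and overwrite a partly answered baseline form, although the total is nearly known in both cases. The harm is mainly lost precision. Bias is possible only through the follow-up forms, if gaps relate to function in ways the other visits do not capture.

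The size is moderate to small: a loss at follow-up bounded by about 3% to 13% of the single-visit standard error over the assumed range, and at baseline about 0.6% to 5% at the middle item rate. The item rates, their independence, item reliability and the baseline/follow-up correlation are all assumptions; the SAP gives none of them. The change is worth making because it is cheap and concerns the proposed primary outcome. For 6.6 the point is only that the scoring should be stated.

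**What to change.** In 5.3.1, and so for 6.1, state that:

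- OSS is scored as 12 times the mean of the answered items when no more than two are blank, and is otherwise missing;
- mean imputation of baseline OSS applies only to forms that remain unscorable, naming the mean used;
- the model is repeated with the strict 12-item complete-case score as a sensitivity analysis, with a matching row in Table 14.

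In 6.6, state that the paired differences and data availability use the same scoring. The comparison of methods in 5.6 and Table 13 can stay as it is.

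Person-mean scoring at two blanks is one of the combinations 5.6 already compares, so this is a choice among the plan's own options. The cost is a few sentences and a line of scoring code that Table 13 already requires. The small downside is reliance on person-mean substitution for one or two items, which the retained complete-case version checks.
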